Mobile Health Intervention to Support Healthful Diet

NCT05236712

December 15th, 2023

STUDY PROTOCOL

Objective

We conducted a pilot randomized controlled trial (RCT) to assess the feasibility and preliminary efficacy of an innovative, theory-driven mobile intervention specifically designed for older adults with frailty, aimed at increasing Mediterranean food consumption. Feasibility was determined by the number of participants enrolled and retained. Primary efficacy outcomes included adherence to the Mediterranean diet score and insulin resistance measures. Secondary and theoretical mechanistic variables involved in behavioral change were food groups, social cognitive theory constructs, and anthropometric and functional measures. Usability and mobile app analytics provided deeper insights into participants' experiences and engagement with the app, identifying potential areas for improvement.

Design

This was a pilot randomized control trial (RCT) to test the feasibility and preliminary efficacy of a mobile intervention consisting of a patient-facing mobile app and a secure web-based administrative dashboard. Participants were randomly assigned to either the intervention group or the control group. Those randomized to the intervention received access to a mobile app, available for download by invitation only on the Apple App Store. Participants randomized to control received via email referral to National Institute on Aging (NIA) materials concerning healthy eating.

Methods

Participants

Study participants were recruited between January and October 2022 through listserv emails, presentations, and flyers in retirement communities and other places frequented by older adults in Seattle, WA. Eligibility criteria included: a) being age 65 years and older, b) having difficulty with at least one of the following activities: performing heavy housework; performing light housework; walking outside alone; managing money/paying bills; shopping for personal items; preparing meals, suggestive of frailty. Exclusion criteria included: a) having difficulty with basic activities of daily living such as eating and getting

out of bed, suggestive of overt disability, b) having a Memory Impairment Screen for Telephone (MIS-T) score of <3, suggestive of memory impairment or cognitive difficulties, c) having a 14-item Mediterranean Diet Adherence Screener (MEDAS) >8, suggestive of an optimal diet, d) severe hearing or visual impairment.

Data Collection Procedures

A study coordinator (SC) collected data during in-person assessments and remotely using standardized procedures at two time points. At the baseline in-person assessment, the SC administered clinical and demographic questionnaires, collected functional and anthropometric measures, and conducted a blood draw using dried blood spot collection methods ([DBS] described later). The second in-person visit occurred about twelve weeks later and included a similar battery of assessments and a recording of a semi-structured exit interview. Moreover, to better understand user engagement and interaction with the mobile health intervention, we collected and analyzed user log data. User log data was automatically captured and stored by the app's backend system, ensuring an accurate and comprehensive collection of user interactions. This data comprised a record of users' actions within the app, including the frequency and duration of use, features accessed, and progress through various intervention components.

STATISTICAL ANALYSIS PLAN

Descriptive statistics were first calculated to compare demographic characteristics between the intervention and the control groups. Outcomes measures were analyzed by calculating the within-group pretest–post-test change scores and then comparing the change scores between the intervention and the control groups using Mann–Whitney U tests. To estimate the magnitude of the intervention's impact compared to the control group, we used Hedges' g to measure effect size. Hedges' g is a variation of Cohen's d that corrects for biases that may occur in small sample sizes, making it a more appropriate choice for our study. Hedges' g takes the difference in means between the intervention and control groups and divides it by the pooled standard deviation while applying a correction factor to account for potential biases. A larger absolute value of Hedges' g indicates a greater effect size, with values of 0.2, 0.5, and 0.8 generally considered small, medium, and large effect sizes, respectively. An R package, "BootES" was used to calculate 95% bootstrap confidence intervals for the effect sizes. The "BootES" package is designed specifically for this purpose, providing a robust and efficient method for estimating confidence intervals based on resampling techniques. Finally, descriptive statistics and visual analytics were used to describe app quality and to analyze log data of user interactions.

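### Does the feasibility objective need a target for enrolment and retention before the counts can be interpreted?

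*Combined protocol and SAP*

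**What the plan says.** The protocol's Objective section describes a pilot randomised trial run "to assess the feasibility and preliminary efficacy of an innovative, theory-driven mobile intervention" and then says: "Feasibility was determined by the number of participants enrolled and retained". The Design section repeats the aim with a different verb: "to test the feasibility and preliminary efficacy of a mobile intervention".

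The facts that bear on the two counts are few. On enrolment, the Participants section gives a window: "Study participants were recruited between January and October 2022 through" the listed channels. On retention, there is one follow-up assessment, in Data Collection Procedures: "The second in-person visit occurred about twelve weeks later".

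The SAP covers baseline description, change scores compared by Mann–Whitney U, Hedges' g with bootstrap intervals, and app data, for which "descriptive statistics and visual analytics were used to describe app quality and to analyze log data of user interactions". It does not mention enrolment or retention. Neither part of the document states a planned sample size, an accrual rate, a retention target or a progression rule.

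**The concern.** Saying that counts determine feasibility, and that the trial tests it, suggests a judgement with two possible outcomes. A judgement needs a criterion, and none is stated. Without a planned sample size, even enrolled against planned cannot be calculated. On this reading any pair of counts could be called feasible, and someone planning a larger trial could not tell a met criterion from a description made afterwards.

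There is a smaller point as well. The word retained is not defined. The Objective says "Primary efficacy outcomes included adherence to the Mediterranean diet score and insulin resistance measures", and at the in-person assessments the coordinator "conducted a blood draw using dried blood spot collection methods". A participant could attend the second visit and still lack an insulin resistance result, so one retained count need not equal the number analysed for each primary outcome.

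**Working it through.** **Is there a figure to reproduce?** No. The documents give no sample size, target, power, alpha or dropout rate. Reading both parts in full for a target, threshold or progression rule finds none. The only benchmarks in the SAP are 0.2, 0.5 and 0.8 for Hedges' g, and those concern efficacy. The factual premise therefore holds: no target is stated in this document.

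**Does the text promise a verdict?** Set the sentences side by side. The Objective speaks of assessing feasibility, and its later sentence on enrolment and retention names the quantities used for that. Read together, the second tells the reader what is measured. The Design section's talk of testing is the stronger wording, but it covers feasibility and preliminary efficacy together and attaches no decision to either. Nowhere does the document say that the intervention is feasible, that it will be declared so, or that a larger trial depends on the answer.

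**Could a target still be added usefully?** Recruitment ended in October 2022. If baseline followed soon after recruitment (an assumption), the last second visit fell about twelve weeks later: 31 October 2022 plus 84 days is 23 January 2023. The document is dated 15 December 2023, nearly eleven months after that. A threshold written at that date would be chosen when the counts could already be known.

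**How much could an unstated target matter?** Only an illustration is possible. Assume 30 randomised and point-estimate cut-offs of 70%, 80% and 90%; none of these figures is in the documents.

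- Retained participants needed: 0.70 × 30 = 21; 0.80 × 30 = 24; 0.90 × 30 = 27. Results from 21 to 26 pass at least one cut-off and fail another.
- Exact binomial chance of passing if true retention is 80% (also assumed): 0.939, 0.607 and 0.123. With 20 randomised it is 0.913, 0.630 and 0.206; with 60 it is 0.978, 0.576 and 0.031.
- Exact (Clopper–Pearson) 95% interval at 80% observed: 16/20, 56% to 94%; 24/30, 61% to 92%; 48/60, 68% to 89%.

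The zone from 21 to 26 is simply the gap between the lowest and highest cut-offs chosen. The same numbers hold for any pilot of that size, so they show no error in this one. Enrolment, the other half of the criterion, cannot be illustrated in this way at all. The interval widths do carry one useful message: at such sizes, an estimate with its interval tells a reader more than a pass or fail.

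**Is the definition of retained in doubt?** There are two time points. The natural reading is completion of the second in-person visit, and an analyst would take it. The number with data for each primary outcome comes out of the change-score analysis, because a change score needs both measurements. App use is described from the logs and is not part of the stated feasibility criterion.

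**The case for a change.** The best case for a change is that the document uses strong words, that feasibility is its first-named objective, and that the remedy is cheap: one sentence saying whether targets were set before recruitment, and a small table. On this view the sponsor may report feasibility descriptively but should say so, since readers may otherwise take the word feasible as the outcome of a test.

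Part of this stands. The document does not state whether targets existed, and saying so would help a reader. But absence from this text does not show that none was set. The document is written after the event and looks abridged: it refers forward to a description of the dried blood spot methods that does not appear. More importantly, the harm arises only if a feasibility claim is made elsewhere without its basis. That would be a question for the report making the claim. No planned analysis would be run differently, and if no target was set the limitation can only be disclosed, not repaired.

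**Conclusion.** No change to the plan is called for. The observation is accurate: no target for enrolment or retention is stated. It amounts to missing detail, however, and the plan as written yields valid counts. No stated figure or result is shown to be wrong, and the efficacy analyses are untouched. The effect on this trial cannot be sized, because every number that could be put to it depends on an assumed sample size, cut-off and true retention.

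The conclusion rests on two readings: that feasibility is being described by the two counts, not put to a pass-or-fail rule, and that retained means completing the second visit at about twelve weeks. On those readings, ordinary reporting closes the gap: number enrolled, and retained over randomised by arm with exact 95% intervals, labelled descriptive. Any target set before recruitment should be reported alongside; none should be invented now. The conclusion would differ if the document itself declared the intervention feasible or made a further trial conditional on these counts. It does neither.

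### Do several primary efficacy outcomes, with no stated significance level or success rule, need a multiplicity provision in this pilot?

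*Combined protocol and SAP*

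**What the plan says.** The Objective section sets the purpose: "We conducted a pilot randomized controlled trial (RCT) to assess the feasibility and preliminary efficacy". Feasibility is judged by the numbers enrolled and retained. On efficacy it says: "Primary efficacy outcomes included adherence to the Mediterranean diet score and insulin resistance measures". Both nouns are plural, the verb leaves the list open, and no analyte or index of insulin resistance is named. The only lead is under Data Collection Procedures, where the coordinator "conducted a blood draw using dried blood spot collection methods ([DBS] described later"; no later description appears in the document.

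The Statistical Analysis Plan treats all outcomes alike, "comparing the change scores between the intervention and the control groups using Mann–Whitney U tests". It then estimates the size of the intervention's impact with Hedges' g, and an R package "was used to calculate 95% bootstrap confidence intervals for the effect sizes". The yardstick is generic: "values of 0.2, 0.5, and 0.8 generally considered small, medium, and large effect sizes, respectively". There is no significance level, order of testing, adjustment or rule for declaring efficacy. Nor is there any statement that the p-values are unadjusted or exploratory.

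**The concern.** Two or more outcomes share primary status, each gets its own test, and nothing says how the results are to be read together. In a confirmatory trial that would be a real defect, because the chance that at least one test is significant under the null rises with each added outcome. The open list makes it look worse: a reader cannot count the primary comparisons, confirm that all were reported, or judge how much one favourable result is worth.

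The same worry applies to the effect sizes without any significance level. If the most favourable of several values of Hedges' g were singled out and carried into the design of a larger trial, it would tend to overstate the effect.

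**Working it through.** The plan states no significance level, power or sample size, so it has no figure of its own to reproduce. The calculation asks how large the problem would be if the silence were filled in the least favourable way.

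**Inputs from the protocol (Objective).** At least two primary efficacy measures; three or more if the plural for insulin resistance is taken literally.

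**Assumptions not in the documents.** Each measure is read at two-sided 5% (critical value 1.96); any one significant result counts as success; there is no true effect; the test statistics are jointly normal with correlation 0 to 0.9.

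**Either direction counted.** The error is 1 − P(all |Z| < 1.96). With independent statistics:
- two measures: 1 − 0.95² = 9.75%
- three measures: 1 − 0.95³ = 14.26%

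**Only results favouring the intervention counted.** The error is 1 − P(all Z < 1.96). With independent statistics:
- two measures: 1 − 0.975² = 4.94%
- three measures: 1 − 0.975³ = 7.31%

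Numerical integration for equally correlated statistics gives:

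| Measures | Correlation | Either direction | Favouring intervention |
|---|---|---|---|
| 1 | – | 5.0% | 2.5% |
| 2 | 0 | 9.75% | 4.9% |
| 2 | 0.5 | 9.1% | 4.5% |
| 2 | 0.9 | 7.0% | 3.5% |
| 3 | 0 | 14.3% | 7.3% |
| 3 | 0.5 | 12.5% | 6.3% |
| 3 | 0.9 | 8.4% | 4.2% |

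A more realistic pattern for three measures is two closely related insulin measures (correlation 0.8 to 0.95) weakly linked to the diet score (0 to 0.3). By simulation this gives 10.8% to 12.4% in either direction and 5.4% to 6.3% in the intervention's favour.

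The last column is the relevant one, since nobody would call a significant worsening of diet or insulin resistance a success. The lower ends are not minimums: at correlation 0.95 the either-direction figures fall to 6.5% and 7.3%.

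These rates belong to normal-theory tests at 5%. They carry over only roughly to reading whether a 95% interval excludes zero. The Mann–Whitney test uses ranks, whereas the bootstrap interval is for a standardised mean difference, and the two can disagree.

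**Effect-size reading.** The documents give no sample size, so 20 per arm is assumed. With no true effect, one Hedges' g has standard error about √(2/20) = 0.316, so its 95% interval spans about ±0.62. The largest of two independent values averages about 0.316/√π = 0.18, and the largest of three about 1.5 × 0.18 = 0.27. At correlation 0.9 these fall to about 0.06 and 0.09. Over 10 to 30 per arm the ranges are 0.05 to 0.26 for two measures and 0.07 to 0.38 for three. At 20 per arm, even the largest of these averages is less than half the half-width of a single interval.

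**Cost of formal control.** Holm's procedure would hold the smallest p-value to 0.025 (two measures) or 0.0167 (three). A measure with 80% power at 0.05, taken only for illustration, would have Φ(1.960 + 0.842 − 2.241) = 71% or Φ(1.960 + 0.842 − 2.394) = 66% at that first step.

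**The case for a change.** The best case for a change does not depend on a significance level. The plan invites readers to set Hedges' g against 0.2, 0.5 and 0.8. With no true effect and 20 per arm assumed, at least one of two measures reaches a favourable g of 0.2 in 32% to 46% of trials, and at least one of three in 35% to 60% (correlation 0.9 to 0). If the insulin measures are never listed, selective emphasis cannot be detected. Describing the aim as preliminary efficacy does not tell readers how to take the p-values. The remedy would cost one list and two sentences.

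Some of this stands. The measures are indeed unlisted, and a report should name and show all of them. But a single measure already reaches 0.2 by chance in about 26% of such trials, since 1 − √(1 − 0.46) = 0.265. Most of that problem is small-sample noise, which the planned intervals display. Selecting the best outcome is a reporting fault that nothing in the plan prescribes.

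A list written now would also settle less than it appears to. "Study participants were recruited between January and October 2022", and the document is dated December 2023 and written in the past tense, so it cannot itself show which measures were fixed before the data were analysed.

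**Conclusion.** The observation is accurate but calls for no change. That the tests are unadjusted is inferred from silence, and the 5% level, the any-one-counts rule, the correlations and the sample size all have to be supplied from outside the documents. Under those assumptions the chance of a false benefit is 3.5% to 4.9% for two measures and 4.2% to 7.3% for three, against 2.5% for one. That inflation would matter if a claim of efficacy rested on it, and the plan makes no such claim.

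For a pilot, separate estimates with intervals and unadjusted tests are a fair choice. Strict family-wise control would cost power and would guard a decision the plan does not take. What is left is missing detail that an analyst fills sensibly: name the insulin measures, report every one, and treat the p-values as exploratory. The conclusion would differ if a report used one significant p-value among these outcomes as evidence that the intervention works; some adjustment across the full set would then be needed.

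### Baseline enters the outcome analysis only by subtraction; one supportive ANCOVA would usually estimate the mean difference a little more precisely (minor)

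*Combined protocol and SAP*

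**What the plan says.** The Statistical Analysis Plan states: "Outcomes measures were analyzed by calculating the within-group pretest–post-test change scores". The arms are then compared by "comparing the change scores between the intervention and the control groups using Mann–Whitney U tests". Magnitude is given by Hedges' g, which "takes the difference in means between the intervention and control groups and divides it by the pooled standard deviation", with a small-sample correction. An R package "was used to calculate 95% bootstrap confidence intervals for the effect sizes". The text does not say whether the means in g are change means or 12-week means, and it does not describe g as adjusted.

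The only baseline comparison described concerns demographics: "Descriptive statistics were first calculated to compare demographic characteristics between the intervention and the control groups". No ANCOVA, regression or other model with baseline as a covariate appears anywhere in the document.

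Both values needed for an adjustment are available. Data Collection Procedures describes a baseline assessment and then: "The second in-person visit occurred about twelve weeks later and included a similar battery of assessments". The Objective adds: "Primary efficacy outcomes included adherence to the Mediterranean diet score and insulin resistance measures".

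**The concern.** Subtracting baseline amounts to fixing the slope of the 12-week value on baseline at 1. When the true slope differs from 1, the change score carries baseline variation that a fitted slope would remove, and the estimated mean difference is noisier than it needs to be.

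Preliminary efficacy is a stated objective, and the reason given for choosing Hedges' g implies a small sample. In addition, the only between-arm estimate described is a unitless g. An adjusted difference in the outcome's own units would usually give a tighter and more readable result for the two primary efficacy outcomes. At stake is a modest amount of precision on data already collected.

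**Working it through.** **Inputs.** The document states no sample size, power, SD or correlation, so there is no figure of its own to reproduce. Assumed: 10 or 20 per arm, 1:1 allocation, rho 0.3 to 0.9, normal data, no effect. From the document: two measurement times about twelve weeks apart, and the exclusion of MEDAS above 8 (Participants).

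**Step 1, equal SDs.** With N participants in total, the variance ratio ANCOVA/change is (1+rho)/2 × (N−3)/(N−4); the second factor is the cost of estimating the slope. The CI-width ratio is its square root times the ratio of t quantiles.
- N = 20, rho 0.5: 0.75 × 17/16 = 0.797; square root 0.893; × 2.110/2.101 gives 0.90.
- N = 40, rho 0.5: 0.75 × 37/36 = 0.771; square root 0.878; × 2.026/2.024 gives 0.88.

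Simulation with 20,000 trials per scenario agrees:

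| | rho 0.3 | 0.5 | 0.7 | 0.9 |
|---|---|---|---|---|
| Width ratio, 10 per arm | 0.83 | 0.90 | 0.95 | 1.01 |
| Width ratio, 20 per arm | 0.82 | 0.88 | 0.94 | 0.99 |
| ANCOVA narrower, 10 per arm | 90% | 80% | 63% | 36% |
| ANCOVA narrower, 20 per arm | 99% | 96% | 85% | 52% |

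**Step 2, unequal SDs.** Let r be baseline SD over 12-week SD. The large-sample width ratio is sqrt[(1−rho²)/(1+r²−2·rho·r)], and the slope is rho/r.
- r = 0.8, rho 0.8: slope 1.0; sqrt(0.36/0.36) = 1.00. Simulated: 1.01 with 20 per arm and 1.03 with 10, so ANCOVA is slightly worse.
- r = 0.8, rho 0.5: simulated 0.96 with 20 per arm and 0.98 with 10.
- r = 1.25, rho 0.3 to 0.9: simulated 0.72 to 0.81 with 20 per arm.

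**Step 3, restricted baseline for the diet score.** If the outcome is MEDAS or a close relative, excluding scores above 8 truncates baseline from above. The slope stays at rho, but the baseline variance falls from 1 to v = 1 − cL − L², where c is the cut in SDs and L is the normal density at c divided by the cumulative probability at c. The large-sample variance ratio becomes (1+rho)/[(1+rho)+(1−rho)v]. The position of the cut is assumed; rho is the correlation before truncation.
- c = +0.8: L = 0.2897/0.7881 = 0.368, v = 0.571. At rho 0.5: 1.5/(1.5+0.285) = 0.840; × 37/36, square root, and t ratio give 0.93.
- c = 0: L = 0.798, v = 0.363. At rho 0.5: 1.5/(1.5+0.182) = 0.892; the same steps give 0.96.

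Simulated width ratios:

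| | rho 0.3 | 0.5 | 0.7 | 0.9 |
|---|---|---|---|---|
| Cut +0.8 SD, 10 per arm | 0.90 | 0.95 | 0.99 | 1.02 |
| Cut +0.8 SD, 20 per arm | 0.89 | 0.93 | 0.97 | 1.00 |
| Cut at mean, 10 per arm | 0.95 | 0.98 | 1.00 | 1.02 |
| Cut at mean, 20 per arm | 0.93 | 0.96 | 0.98 | 1.01 |

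With 10 per arm, rho 0.7 and the +0.8 SD cut, ANCOVA was the narrower interval in 48% of trials.

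**Step 4, power (0.75 SD effect, 20 per arm; Mann–Whitney on change against permutation ANCOVA).** Normal errors: 62% vs 74% at rho 0.5 and 83% vs 89% at rho 0.7. Heavy-tailed t(3) errors: 76% vs 82% at rho 0.5, but 94% vs 91% at rho 0.7 and 99% vs 95% at rho 0.8. Type I error was 3.8% to 5.8% throughout. This sets a rank test against a model for the mean, so it is secondary to the width ratios.

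**Step 5, what adjustment does not touch.** With no effect, the mean width of the percentile bootstrap CI for g on change is 1.26 to 1.27 with 20 per arm and 1.85 to 1.86 with 10, at every rho from 0.3 to 0.9. Standardising by the SD of the change removes the dependence on rho, so the ratios above do not carry over to that interval.

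**The case against.** The strongest reply is that nothing here is wrong. A Mann–Whitney test on change is valid under randomisation. The trial is a pilot whose feasibility is judged by enrolment and retention, and no efficacy decision rule depends on the precision. That stands, and it sets the grade.

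The reply on size also stands. The equal-SD figures overstate the gain for one of the two primary outcomes if the eligibility limit truncates its baseline. Distribution and correlation are unknown, and with heavy tails and high rho the planned test can have more power.

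A reader might infer that chance baseline imbalance makes the reported g misleading. If g is computed on change, which the text does not state, a one-SD chance imbalance with 20 per arm moves it by sqrt((1−rho)/2) × sqrt(2/n), with n per arm: at rho 0.5, 0.5 × 0.316 = 0.16. But that shift averages to zero over trials, and it is already part of the sampling variation that the interval for g reflects (half-width about 1.26/2 = 0.63). It accounts for (1−rho)/2 = 25% of the variance of g at rho 0.5. A supportive ANCOVA leaves g as it is, so this argument does not support the fix.

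It is also fair to say that an unadjusted mean difference would supply an estimate in natural units. The remaining case for adjustment is precision alone.

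**Conclusion.** The point holds as a minor efficiency comment. The plan uses baseline only by subtraction and describes no adjusted analysis. With 10 to 20 per arm, equal SDs and normal data, ANCOVA would narrow the 95% CI for the mean difference by about 17-18%, 10-12% and 5-6% at rho 0.3, 0.5 and 0.7. For a diet score with restricted baseline (assumed cut between +0.8 SD and the mean) the figures are about 5-11%, 2-7% and 0-3%. The gain vanishes or slightly reverses near rho 0.9 or when the slope is near 1. Every one of these figures rests on assumed inputs.

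The documents do not support reading this as a flaw in validity, as bias in g, or as a reason to replace the stated test.

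**What to change.** Keep the Mann–Whitney test and Hedges' g as the stated analysis. Beside them, report for every outcome, not a selection, one ANCOVA of the 12-week value on arm plus the baseline value of the same measure. Give the adjusted mean difference in the outcome's own units with a 95% CI. Given the small sample, use bootstrap or permutation-based inference; a permutation should follow the allocation scheme actually used.

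For skewed measures, choose the scale from pooled data without reference to arm results. The insulin resistance measures are not defined in the document, so a log scale cannot be prescribed for all of them.

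The document reports the analysis as already done, so label the addition post hoc and supportive, and state that it does not override the stated test if the two disagree.

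Cost: one degree of freedom and a second result for each outcome. No new data are needed.
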